3.2. Minimization of Bias

3.2.1. Randomization

Patients will be allocated to a randomized treatment sequence (Arm A: KZR-616 followed by placebo; Arm B: placebo followed by KZR-616) in a 1:1 fashion. Patients will receive the first assigned study drug treatment in Treatment Period 1 (W0 through before dosing at W16)

and cross over to receive the next study drug treatment beginning on the first day of Treatment Period 2 (administration of the first dose at W16 through W32). Patients will be stratified according to their diagnosis of PM or DM. Patients will be stratified by their diagnosis of DM or PM.

3.2.2. Blinding

This is a double-blind study. The Sponsor, Investigator, study personnel, and patients will not make any efforts to determine which study drug is being received. Unblinded pharmacy (or other qualified site) personnel will be utilized in this study to prepare the study drug, and unblinded study personnel (eg, Clinical Pharmacologist required for conducting any PK analyses and Statistician) may be utilized in this study.

3.2.3. Breaking the Blind

If the treatment allocation for a patient becomes known to the Investigator or other study staff involved in the management of study patients, the Sponsor must be notified immediately by the Investigator.

Patients should not be routinely unblinded to treatment assignment. Only in the case of an emergency, when knowledge of the study drug is essential for the clinical management or welfare of a specific patient, may the Investigator unblind a patient's treatment assignment. The unblinding of the patient's treatment assignment can be completed through the use of the electronic data capture (EDC) Randomization and Trial Supply Management (RTSM) system to determine treatment and institute appropriate follow-up care. However, prior to any unblinding, the Investigator is strongly advised to discuss options with the Medical Monitor or appropriate Sponsor study personnel. As soon as possible and without revealing the patient's study treatment assignment (unless important to the safety of patients remaining in the study), the Investigator must notify the Sponsor if the blind is broken for any reason. The Investigator will record in source documentation the date and reason for unblinding and the names and roles of personnel unblinded. The reason for unblinding will be captured directly within the EDC system prior to the unblinding as well. The EDC system will automatically store the date and time of the unblinding.

All unblinding events (with the exception of those by pharmacovigilance for regulatory reporting purposes) must be reported to the Sponsor's Medical Monitor and designee promptly.

Patients who have been unblinded for pharmacovigilance reporting purposes only will not, based on the unblinding alone, be discontinued from further receipt of investigational product.

3.3. Number of Sites

Up to approximately 18 sites are planned to participate in this study.

4. PATIENT SELECTION AND ENROLLMENT

4.1. Number of Patients

Approximately 24 patients are planned for enrollment. It is anticipated that 40 patients will be screened to achieve 24 patients enrolled.

4.1.1. Patient Screening

Study participation begins once written informed consent is obtained (see [Section 11.3](#) for details). The Investigator will ensure that the patient has provided written informed consent before performing any study-related assessments.

Once informed consent is obtained, a sequential patient identification number will be assigned by the site, and the screening evaluations may begin to assess study eligibility (inclusion/exclusion) criteria. The patient identification number will be used to identify the patient during the screening process and throughout study participation, if applicable.

Screening assessments (see the Schedule of Assessments [[Table 2](#)]) for this study should be performed between Day -28 and Day -1. The Screening Period can be extended to 35 days upon Sponsor or designee approval only. Patients who fail Screening or do not meet inclusion/exclusion criteria may be rescreened 1 time.

Only individuals who fulfill all of the inclusion criteria and none of the exclusion criteria may be enrolled into the study. Data collected at Screening will be reviewed by the Sponsor, designee(s), or adjudication committee (as defined in the Study Manual) to confirm eligibility, of the patient to be enrolled.

4.2. Inclusion Criteria

1. Adult patients must be at least 18 years of age at the time of signing informed consent at Screening
2. Body Mass Index (BMI) of 18 to 40 kg/m²
3. Diagnosis of probable or definite DM or PM by the 2017 European League Against Rheumatism (EULAR)/American College of Rheumatology (ACR) Classification Criteria
4. Must have their data reviewed by an adjudication committee to confirm eligibility unless at least 1 of the following is present:
 - a. Muscle biopsy with evidence of active myositis within the last 6 months prior to or at Screening
 - b. Electromyography or magnetic resonance imaging (MRI) with evidence of active myositis within the last 6 months prior to Screening
 - c. A CK $\geq 4 \times$ upper limit of normal (ULN).
5. Must have demonstrable muscle weakness as measured by the MMT-8 with a score $\geq 80/150$ but $\leq 136/150$ units and any 2 of the following:
 - a. MDGA visual analog scale (VAS) ≥ 2 cm
 - b. PtGADA VAS ≥ 2 cm

- c. At least one muscle enzyme laboratory measurement (ie, CK, aldolase, LDH) $\geq 1.3 \times$ ULN
- d. MDAAT Extramuscular Global Activity VAS ≥ 1 cm.
- 6. Documented inadequate response to a 12-week trial of corticosteroids or at least 1 immunosuppressant (eg, MTX, MMF, mycophenolate sodium [MPS], AZA, leflunomide [LEF], tacrolimus, CyA) OR have demonstrated significant documented toxicity or intolerance to such therapies
- 7. Has had age-appropriate cancer screening that is up to date and negative for evidence of malignancy as per local standard of care (see [Appendix A](#))
- 8. Female patients of childbearing potential must have a negative serum pregnancy test at Screening and a negative urine pregnancy test at Baseline and must agree to employ adequate birth control measures for the duration of the study. Women of childbearing potential (WOCBP) must use highly effective and medically acceptable methods of contraception to prevent pregnancy during Screening and must agree to continue to practice adequate contraception during the study and for 4 weeks after administration of the last dose of the study drug.
For the purposes of this study, WOCBP are defined as: all postpubescent female patients, unless the patient is postmenopausal (defined by amenorrhea for at least 2 years or amenorrhea for at least 1 year with confirmatory follicle stimulating hormone [FSH] level in the postmenopausal range as documented historically or measured by the central laboratory at Screening and if patient is not on supplementary hormonal therapy) or if the patient is surgically sterile (ie, tubal ligation, hysterectomy, bilateral salpingoophorectomy).
Highly effective contraception is defined as the use of 2 barrier methods (eg, female diaphragm and male condom), 1 barrier method with spermicide, intrauterine device, or hormonal contraceptives (eg, implant or oral). If using a hormonal form of contraception, use must have been stable for at least 4 weeks prior to Screening, and if using concomitant mycophenolate, the patient must use another nonhormonal form of highly effective contraception. Abstinence will be acceptable only if it is in line with the preferred and usual lifestyle of the patient. Periodic abstinence (eg, calendar, ovulation) and withdrawal are not acceptable methods of contraception
- 9. Male patients must be either congenitally sterile surgically sterile (vasectomy with documented confirmation of aspermia) or willing to use a condom in addition to having their female partner use another form of contraception (such as an intrauterine device, barrier method with spermicide, or hormonal contraceptive [eg, implant, injectable, patch, or oral]) from Screening until 12 weeks after administration of the last dose of the study drug, unless their partners are infertile or surgically sterile
- 10. Willing and able to comply with the requirements of the protocol
- 11. Provide written informed consent prior to any study-related procedure.

4.3. Exclusion Criteria

- 1. Has significant muscle damage (eg, severe muscle atrophy, end-stage disease, postmyopathic DM) per Investigator opinion or has a muscle damage VAS score ≥ 5 cm on the MDI
- 2. Any other form of myositis or myopathy other than PM or DM (eg, metabolic or drug-induced myopathy, drug-induced myositis, juvenile PM or DM, inclusion body

myositis, cancer-associated myositis [myositis diagnosed within 3 years, either before or after, of a diagnosis of any malignancy except for squamous or basal cell carcinoma of the skin or cervical carcinoma in situ], myositis in overlap with another connective disease [eg, SLE, systemic sclerosis, RA], or muscular dystrophy); patients with secondary Sjogren's syndrome, necrotizing myopathy, or antisynthetase syndrome are permitted to participate in this study

3. Any condition (eg, severe arthritis with limited range of motion or severe calcinosis) that, in the Investigator's opinion, precludes the ability to quantitate muscle strength
4. Has severe interstitial lung disease per Investigator opinion or has a pulmonary damage VAS score ≥ 5 cm on the MDI
5. Presence of autoinflammatory disease (eg, psoriatic arthritis, axial spondyloarthropathy, inflammatory bowel disease)
6. Has received treatment with any of the following:
 - a. Oral prednisone (or prednisone equivalent) doses >20 mg/day at Screening or during the Screening Period, or initiation of oral prednisone during the Screening Period. If oral prednisone is being used at Screening, use should be stable during the 2 weeks prior to Baseline
 - b. Use of nonsteroidal immunosuppressants other than oral MMF or MPS (≤ 3 g/day or 2160 mg/day, respectively); oral, intramuscular (IM), or SC MTX (≤ 25 mg/week); AZA (≤ 2.5 mg/kg/day); LEF (≤ 20 mg/day); tacrolimus (≤ 3 g/day); or concurrent use of more than 1 nonsteroidal immunosuppressant at Baseline. If a permitted nonsteroidal immunosuppressant is being used, it must have used for at least 12 weeks and must have been taken at a stable dose (including stable route of administration) for the last 4 weeks prior to Screening. If MMF, MPS, MTX, AZA, LEF, or tacrolimus is being discontinued, it must be discontinued at least 4 weeks prior to Baseline
 - c. Antimalarials exceeding the recommended doses (hydroxychloroquine up to 400 mg/day or 6.5mg/kg/day, whichever is less; chloroquine up to 250 mg/day, or quinacrine up to 100 mg/day are permitted) or taken at an unstable dose during the 12 weeks prior to Screening. If an antimalarial is being discontinued, it must be discontinued at least 4 weeks prior to Baseline. Antimalarials are considered distinct from corticosteroids in (a) and nonsteroidal immunosuppressants in (b) above
 - d. Initiation of or use of an unstable dose of topical therapy (eg, corticosteroids, pimecrolimus) in the 4 weeks prior to Screening. If topical therapy is being discontinued, it must be discontinued at least 4 weeks prior to Baseline.
7. Receipt of any of the following treatments within the following time frames before Screening:
 - a. Oral corticosteroids at doses ≥ 1 mg/kg/day prednisone or equivalent: 4 weeks
 - b. Intravenous or IM corticosteroids: 4 weeks
 - c. Intra-articular therapies, such as corticosteroids or hyaluronic acid preparations: 4 weeks
 - d. Intravenous, SC, or IM Ig: 4 weeks
 - e. Cyclophosphamide or chlorambucil: 24 weeks
 - f. Prohibited nonbiologic nonsteroidal immunosuppressants or targeted therapies including, but not limited to, CyA, dapsone, tofacitinib, baricitinib: 8 weeks

- g. Cytokine or integrin antagonists or selective costimulation modulators including, but not limited to, interleukin (IL)-1, IL-6, IL-17, IL-12/23, IL-23, interferon (IFN), integrin, and tumor necrosis factor (TNF) α antagonists or abatacept: 12 weeks
- h. B cell-depleting or modulating therapies (eg, rituximab, ofatumumab, obinutuzumab, ocrelizumab, belimumab, atacicept): 24 weeks
For those patients who have used an anti-CD20 drug at \geq 24 weeks and $<$ 48 weeks before Screening, they must have levels of circulating CD19+ B cells \geq the lower limit of normal (LLN). A CD19 count is not required for patients with prior use of an anti-CD20 drug \geq 48 weeks prior to Screening
- i. Previous treatment with the following cell-depleting therapies, including investigational agents or approved therapies: alemtuzumab, anti-CD4, anti-CD5, or anti-CD3: at any time
- j. Other biologics or investigational drugs: 8 weeks or 5 half-lives, whichever is longer
- k. Transfusion with blood, packed red blood cells, or platelets or treatment with plasmapheresis or plasma exchange: 6 weeks
- l. Creatine dietary supplements: 4 weeks.

8. Initiation of an exercise program (including physical therapy or occupational therapy) for muscle strengthening within 4 weeks of Screening or initiation planned during the study. Any exercise program or regimen that was initiated $>$ 4 weeks prior to Screening must be continued in a stable manner during Screening and the study
9. Patient has had recent serious or ongoing infection, or risk for serious infection, including:
 - a. Acute or chronic infection defined as any infection requiring systemic antibiotic, antifungal, or antiviral (antimicrobial) therapy within 2 weeks of Baseline
 - b. Hospitalization or receipt of a course of IV antimicrobial therapy within 24 weeks prior to Screening or during the Screening Period
 - c. Symptomatic herpes zoster or herpes simplex infection (HSV) (not including simple oral HSV lesions) within 12 weeks prior to Screening or during the Screening Period
 - d. History of severe and/or disseminated viral infections, and/or opportunistic infections
 - e. Known seropositivity for or active infection by human immunodeficiency virus (HIV)
 - f. Active, chronic, or resolved hepatitis B or hepatitis C infection (hepatitis B core antibody or surface antigen positive, or hepatitis C antibody positive at Screening)
 - g. History of progressive multifocal leukoencephalopathy
 - h. Active or untreated latent tuberculosis (TB), as suggested by chest radiograph performed within the 12 weeks prior to or at Screening (see [Section 7.2.6.3](#)) or positive (or 2 indeterminate or borderline) results of an approved TB test at Screening (see [Section 7.2.6.1](#)). Patients with a history of latent TB with documented completed treatment per Centers for Disease Control and Prevention guidelines and no known exposures post treatment are allowed to participate
 - i. Receipt of a live-attenuated vaccine within 4 weeks of Screening

- j. Primary immunodeficiency (unless otherwise considered, in the opinion of the Investigator or the Sponsor, to confer a clinically insignificant infection risk, such as deficiency in IgA, C1q, C2, or C4 without a history of recurrent infections [3 or more infections in 1 year that required antimicrobial therapy])
- k. History of recurrent infections [3 or more infections in 1 year that required antimicrobial therapy] in the 12 months prior to Baseline
- l. Prior hematopoietic cell or solid organ transplant.
10. History of any concurrent illness (eg, asthma) that has required treatment with oral or parenteral corticosteroids for more than a total of 2 weeks within the last 24 weeks prior to Screening
11. Any of the following laboratory values at Screening:
 - a. Estimated glomerular filtration rate <45 mL/min by CKD-EPI (Chronic Kidney Disease Epidemiology Collaboration) equation
 - b. Hemoglobin <10 g/dL
 - c. White blood cell (WBC) count <3.0 × 10⁹/L
 - d. Absolute neutrophil count (ANC) <1.5 × 10⁹/L (1500/mm³)
 - e. Platelet count <100 × 10⁹/L
 - f. Serum AST or serum ALT >2.5 × ULN (unless considered consistent with muscle origin)
 - g. Serum alkaline phosphatase >2.5 × ULN
 - h. Total bilirubin >1.5 × ULN (3 × ULN for patients with documented Gilbert's syndrome)
 - i. Thyroid stimulating hormone outside of the central laboratory normal range
 - j. IgG <500 mg/dL.
12. Presence of New York Heart Association Class III or IV heart failure, or uncontrolled blood pressure (systolic blood pressure ≥160 mm Hg or diastolic blood pressure ≥100 mm Hg at rest), or QT interval with Fredericia's correction (QTcF) or Bazett's correction (QTcB) >480 msec on ECG
13. Major surgery within 12 weeks before Screening, major surgery planned during the study period, or any surgery planned during the study period that would require an alteration of concomitant immunosuppressant or corticosteroid therapy or additional corticosteroid therapy
14. Clinical evidence of significant unstable or uncontrolled diseases (eg, cardiac [including congestive heart failure, hypertension, angina, or recent {<6 months prior to Screening} myocardial infarction], pulmonary [including chronic obstructive pulmonary disease, asthma requiring systemic corticosteroid therapy, pulmonary hypertension, or interstitial lung disease], hematologic, gastrointestinal, endocrinologic [eg, hypothyroidism, diabetes], hepatic, renal, neurological, or infectious) that, in the opinion of the Investigator or Sponsor, could confound the results of the study, put the patient at undue risk, or interfere with protocol adherence
15. Evidence of current or previous clinically significant disease, medical condition (including abnormal laboratory values), or finding in the medical examination that in the Investigator's or Sponsor's opinion would compromise the safety of the patient or the ability to interpret the data
16. Any active or suspected malignancy, including myeloproliferative or lymphoproliferative disorder, or history of documented malignancy within the last

5 years before Screening or within 3 years of diagnosis of myositis, except appropriately excised and cured cervical carcinoma in situ or basal or squamous cell carcinoma of the skin; patients with a history of basal or squamous cell carcinomas of the skin must have had 3 or fewer in their lifetime to be eligible

- 17. Alcohol abuse or drug abuse in the last 1 year prior to Screening in the opinion of the Investigator
- 18. Women who are pregnant, lactating, or discontinued lactation less than 12 weeks prior to Screening, or women who plan to become pregnant or initiate lactation during the study
- 19. Patients who are unable to comply with the protocol in the Investigator's or Sponsor's opinion.

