1. Has significant muscle damage (eg, severe muscle atrophy, end-stage disease, postmyopathic DM) per Investigator opinion or has a muscle damage VAS score ≥ 5 cm on the MDI
2. Any other form of myositis or myopathy other than PM or DM (eg, metabolic or drug-induced myopathy, drug-induced myositis, juvenile PM or DM, inclusion body myositis, cancer-associated myositis [myositis diagnosed within 3 years, either before or after, of a diagnosis of any malignancy except for squamous or basal cell carcinoma of the skin or cervical carcinoma in situ], myositis in overlap with another connective disease [eg, systemic lupus erythematosus {SLE}, systemic sclerosis, rheumatoid arthritis {RA}], or muscular dystrophy); patients with secondary Sjogren's syndrome, necrotizing myopathy, or antisynthetase syndrome are permitted to participate in this study
3. Any condition (eg, severe arthritis with limited range of motion or severe calcinosis) that, in the Investigator's opinion, precludes the ability to quantitate muscle strength
4. Has severe interstitial lung disease per Investigator opinion or has a pulmonary damage VAS score ≥ 5 cm on the MDI
5. Presence of autoinflammatory disease (eg, psoriatic arthritis, axial spondyloarthropathy, inflammatory bowel disease)
6. Has received treatment with any of the following:
 - a. Oral prednisone (or prednisone equivalent) > 20 mg/day at Screening or during the Screening Period, or initiation of oral prednisone during the Screening Period. If oral prednisone is being used at Screening, use should be stable during the 2 weeks prior to Baseline
 - b. Use of nonsteroidal immunosuppressants other than oral MMF or MPS (≤ 3 g/day or 2160 mg/day, respectively); oral, intramuscular (IM), or SC MTX (≤ 25 mg/week); AZA (≤ 2.5 mg/kg/day); LEF (≤ 20 mg/day); tacrolimus (≤ 3 g/day); or concurrent use of more than 1 nonsteroidal immunosuppressant at Baseline. If a permitted nonsteroidal immunosuppressant is being used, it must have used for at least 12 weeks and must have been taken at a stable dose (including stable route of administration) for the last 4 weeks prior to Screening. If MMF, MPS, MTX, AZA, LEF, or tacrolimus is being discontinued, it must be discontinued at least 4 weeks prior to Baseline

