6.2.1. Permitted Concomitant Medications

6.2.1.1. Myositis Disease-related Concomitant Medications

Patients should continue all concomitant medications related to myositis therapy throughout the study, as outlined in the Inclusion/Exclusion Criteria ([Section 4.2](#) and [Section 4.3](#)) at a stable dose, without modification throughout the study, unless there is documented toxicity, intolerance, or lack of availability. No new immunomodulatory therapies, including investigational agents, are permitted to be introduced during the study. If a concomitant treatment for myositis needs to be decreased or discontinued for safety reasons, the reason must be documented in the eCRF and should be discussed with the Medical Monitor (and discussed in advance where possible).

The permitted medications for myositis include the use of the following:

- Oral prednisone (or prednisone equivalent) dose ≤ 20 mg/day. If used, it must have been present at Screening, used at a stable dose for the 2 weeks prior to Baseline.
- The use of a maximum of 1 of the following immunosuppressants is allowed:
 - Oral MMF or MPS (≤ 3 g/day or 2160 mg/day, respectively)
 - Oral, IM, or SC MTX (≤ 25 mg/week)
 - Oral AZA (≤ 2.5 mg/kg/day)
 - LEF (≤ 20 mg/day)
 - Tacrolimus (≤ 3 g/day).

If a permitted immunosuppressant is being used, it must have been used for at least 12 weeks and must have been taken at a stable dose (including stable route of administration) for the last 4 weeks prior to Screening.

- The use of the following antimalarials is allowed if present at a stable dose for at least 12 weeks prior to Screening:
 - Hydroxychloroquine up to 400 mg/day or 6.5 mg/kg/day, whichever is less
 - Chloroquine up to 250 mg/day
 - Quinacrine up to 100 mg/day.
- Continued use of a stable dose of topical therapy (eg, corticosteroids, pimecrolimus) is allowed.

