6.2.3. Restricted or Prohibited Therapies

Use of the following is prohibited during the study and as described in [Section 4.3](#):

- Oral prednisone (or prednisone equivalent) doses >20 mg/day
- Intravenous or IM corticosteroids
- Initiation of IV, SC, or IM Ig
- Immunosuppressants (other than as presented in [Section 6.2.1](#))
- Antimalarials at doses that exceed the recommended dose (see [Section 6.2.1](#))
- Topical therapy (other than as presented in [Section 6.2.1](#))
- Intra-articular therapy (eg, corticosteroids or hyaluronic acid preparations)
- Cyclophosphamide or chlorambucil
- Nonbiologic immunosuppressants or targeted therapies including, but not limited to, CyA, dapsone, tofacitinib, baricitinib
- Cytokine or integrin antagonists or selective costimulation modulators including, but not limited to, IL-1, IL-6, IL-17, IL-12/23, IL-23, IFN, integrin, and TNF α antagonists or abatacept
- B cell-depleting or modulating therapies (eg, rituximab, ofatumumab, obinutuzumab, ocrelizumab, belimumab, atacicept)
- Cell-depleting therapies, including investigational agents or approved therapies, alemtuzumab, anti-CD4, anti-CD5, or anti-CD3
- Any other biologics or investigational drug(s)
- Transfusion with blood, packed red blood cells, or platelets or treatment with plasmapheresis or plasma exchange
- Creatine dietary supplements
- Live-attenuated vaccines
- Major surgery during the study period, or any surgery planned during the study period that would require an alteration of concomitant immunosuppressant or corticosteroid therapy or additional corticosteroid therapy.

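### The tacrolimus ceiling is written as 3 g/day in all three places that state it, matching the mycophenolate mofetil cap, so in practice it does not limit tacrolimus dose

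*Combined protocol and SAP*

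**What the plan says.** Three places state a tacrolimus ceiling, and they agree:

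- Synopsis, exclusion 6b: "tacrolimus (≤ 3 g/day); or concurrent use of more than 1 nonsteroidal immunosuppressant at Baseline".
- Section 4.3, exclusion 6b: "tacrolimus (≤ 3 g/day".
- Section 6.2.1.1, permitted myositis medications: "Tacrolimus (≤ 3 g/day".

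The entry that opens the list in Section 4.3 is "oral MMF or MPS (≤ 3 g/day or 2160 mg/day, respectively", repeated in Section 6.2.1.1. The other caps are 25 mg/week for methotrexate (MTX), "AZA (≤ 2.5 mg/kg/day" for azathioprine, and 20 mg/day for leflunomide (LEF).

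For the treatment period, Section 6.2.3 prohibits "Immunosuppressants (other than as presented in" Section 6.2.1, so the on-study limit is taken by reference from the same list. Topical treatment is handled separately in exclusion 6d: "Initiation of or use of an unstable dose of topical therapy (eg, corticosteroids, pimecrolimus" and similar products.

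**The concern.** Exclusion 6b is built so that each permitted agent has a dose limit, which shows an intention to restrict background immunosuppression at entry. A tacrolimus limit at gram level, identical to the MMF limit, looks like a unit error (g typed for mg) or the MMF figure carried down the list. If so, the tacrolimus entry restricts nobody.

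What is at stake is eligibility and background therapy. Section 4.1.1 has the sponsor, a designee or the adjudication committee review Screening data to confirm eligibility, but they would be checking against the same figure, so that review would not by itself stop a high dose.

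**Working it through.** The plan derives no figure here, so the check is a comparison of the text plus unit conversion.

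**1. Is it one slip or a consistent value?** All three statements give 3 g/day. No section gives a tacrolimus limit in mg, a blood-level limit or a correction. The agreement is weak evidence of intent: exclusion 6b in the synopsis and in Section 4.3 share the same missing word in the sentence on 12 weeks of prior use, so the text appears to have been copied from one to the other, and an error would travel with it.

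**2. Could it be an ointment quantity?** No. Topical therapy has its own item (6d) and its own bullet in Section 6.2.1.1. Section 6.2.2 also lists topical calcineurin inhibitors apart from nonsteroidal immunosuppressants. The tacrolimus entry sits among the latter.

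**3. Where does the figure sit in the protocol's own list?** 3 g/day = 3000 mg/day.

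| Agent | Cap in the protocol | 3000 mg/day relative to it |
|---|---|---|
| MMF | 3 g/day = 3000 mg/day | 3000 / 3000 = 1 |
| Mycophenolate sodium (MPS) | 2160 mg/day | 3000 / 2160 = 1.39 |
| LEF | 20 mg/day | 3000 / 20 = 150 |
| MTX | 25 mg/week; 25 / 7 = 3.57 mg/day | 3000 / 3.57 = 840 |

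These ratios do not compare potency. They show only that the tacrolimus figure lies on the mycophenolate scale and coincides with the MMF entry.

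**4. Does the ceiling bind?** The documents give no usual tacrolimus dose. Assumption: systemic doses of 1 to 30 mg/day.

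- Top of the range: 3000 / 30 = 100.
- Bottom of the range: 3000 / 1 = 3000.

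The ceiling is 100 to 3000 times the dose in use. The assumed maximum could be too low by a factor of almost 100 and the ceiling would still exclude no one.

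**5. What if only the unit is wrong?** The ceiling becomes 3 mg/day, which is 3000 / 3 = 1000 times lower than written, and users above 3 mg/day become ineligible. If the MMF entry was copied instead, the intended value cannot be recovered from the documents.

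**6. What still restricts tacrolimus users?** Only one such agent is allowed; it must have been used for at least 12 weeks, with dose and route stable for the 4 weeks before Screening (Sections 4.3 and 6.2.1.1). During the study the dose may not be changed except for toxicity, intolerance or supply problems (Section 6.2.1.1), and an increase counts as rescue (Section 6.2.2). None of these is a dose ceiling at entry.

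**The case against.** The strongest reply is that the documents do not themselves show 3 g/day to be wrong. They contain no tacrolimus dose, so the last step uses an outside assumption about dosing. That is true, and it is why the cause is given only as probable. The conclusion that the ceiling does not bind is less exposed, because it survives an almost 100-fold error in the assumed maximum.

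A second reply is that the reach is narrow. Stable dosing is required on study and increases are rescue, so a patient's entry dose already acts as the on-study limit. This stands: the defect matters mainly at entry, and the reference in Section 6.2.3 adds little beyond repeating it.

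Third, other criteria in Section 4.3 limit the safety consequence: exclusion 15 (clinically significant conditions or findings, including abnormal laboratory values, at the investigator's or sponsor's judgement), exclusion 9l (transplant history) and exclusion 11a (eGFR below 45 mL/min). They do narrow it, but none supplies a tacrolimus dose limit.

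Finally, there may be no tacrolimus users among about 24 patients, and nobody is dosed from this figure. Both points bear on how much this matters, not on whether the threshold works as written.

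**Conclusion.** The concern holds. The tacrolimus ceiling is stated identically in three places, equals the MMF cap, and has no reading in the text that rescues it. On the assumption of systemic doses between 1 and 30 mg/day it stands at least 100-fold above any dose in use and excludes no tacrolimus user. Confidence is high that the ceiling is ineffective; the intended value is not known.

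The consequence is limited to one missing dose limit on background therapy. Sample size, power and the within-patient primary analysis are unaffected. It should be corrected because an explicit eligibility threshold does not do what it was written to do, and the correction is cheap.

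**What to change.** Ask the sponsor's medical team to confirm the intended tacrolimus ceiling in milligrams; if only the unit is wrong, it is 3 mg/day. Enter the confirmed value identically in synopsis exclusion 6b, Section 4.3 exclusion 6b and Section 6.2.1.1. Section 6.2.3 then follows by reference.

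Notify sites and check any tacrolimus users already screened. List enrolled patients above the corrected limit for information; they met the criterion in force when they entered. Do not lower a dose merely to comply, since Section 6.2.1.1 requires stable background treatment.

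The cost is a wording correction in three places, a site memo and a short data check; Section 6.2 already requires concomitant medication doses to be recorded. The downside is that some tacrolimus users may become ineligible. How many depends on the confirmed value and on doses in the screened population, which the documents do not give.
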